10.2 Clinical data management

Clinical data management (CDM) enables the generation of high-quality, reliable, and statistically valuable data. CDM is the process of collecting, cleaning, and managing subject information in a study in compliance with regulatory standards (21 CFR Part 11, ICH, and GCP guidelines). It covers eCFR design, eCFR commenting, database design, *data entry*, validation (*Source Document Verification* (SDV)), discrepancy handling (*queries*), medical coding (*medical coding*), extraction (*soft lock*) and closing the database (*hard lock*).[54]

In accordance with roles and responsibilities, multiple users can be created, whose access types to the eCRF can be limited to data entry (principal investigator, PI), medical coding, database design, or quality control. *check* [54, 55] Discrepancy handling will be based on the flow in Figure 5.

The CDM team will include the following roles:

- Data Manager
- Database Designer/Programmer
- Clinical coder (*Medical coder*)
- Clinical Data Coordinator
- Quality control
- *Data entry associate*)

[figure not shown]

Figure 5Discrepancy management (DCF, medical note; CRA, clinical monitor; SEC, *self-evident*) correction) [54]

10.3 Statistical methodology

The statistical analysis plan was developed considering the evaluation criteria described in the study protocol.

Statistical analysis will be performed by personnel from Laboratorios Sophia, SA de CV. Specialized statistical software will be used (SPSS statistical package, available version, or R software). Coding will be performed using consecutive numbers. Data will be collected and organized in an Excel spreadsheet (Microsoft® Office). The data will then be exported to the specialized statistical software. Variables will be categorized according to their nature (see Table 3). The statistical tests used will follow the corresponding assumptions for nonparametric statistics.

10.3.1 Population analysis

Statistical analysis will be presented to provide a general overview of the subjects enrolled in the study and an overview of the safety and tolerability of the results. Data provided by the research

site will be summarized for this purpose, according to their nature. The Shapiro-Wilk test will be performed to test whether the quantitative data are normally distributed.

The results of the quantitative variables will be presented as measures of central tendency: mean, standard deviation, maximum, and minimum. Changes in pupil diameter, BCVA, and body temperature will be expressed as continuous variables. Changes in IOP, HR, systemic blood pressure, TVL, and TF will be expressed as discrete variables.

The results of nominal and ordinal qualitative variables will be presented as frequencies, proportions, and/or percentages. For these, 2 x 2 frequency tables will be constructed. All percentages will be presented with one decimal place.

The level of difference considered significant will be an alpha (α) of 0.05 or less. The triangulation between the type of variable and the measurements is shown in Table 6 .

Table vi. Triangulation of concepts

Variable type	Variable	A1	A2	B1	B2	C1	C2	C3	C4	D1	D2	D3	D4	E1	E2
Selection															
A1	Demographics	DT													
A2	Medical history/Selection criteria		DT												
Basal															
B1	Vital signs		B	B		B		B	T				TM		
B2	Comprehensive ophthalmological evaluation		DTB		TB	B									
Security															
C1	PIO				B	B							TM		
C2	HR, SBP, DBP			B			B						TM		
C3	Pupillary diameter			B			B						TM		
C4	Conjunctival hyperemia			T				T					T		
Secondary Safety Outcome															
D1	AVMC				B					B			TM		
D2	Corneal and conjunctival stains			B						B			TM		
D3	Chemosis			T							T	T			
D4	Incidence of AE		TM	TM	TM	TM	TM	T	TM	TM	T	TM	TM	TM	TM
Exploratory															
E1	FR			B									TM	B	
E2	Body temperature		B										TM		B

Abbreviations: BCVA, best-corrected visual acuity; B, bivariate analysis; D, descriptive statistics; AE, adverse event; HR, heart rate; RR, respiratory rate; M, multivariate analysis; DBP, diastolic blood pressure; SBP, systolic blood pressure; IOP, intraocular pressure; T, 2x2 contingency table.

10.3.2 Safety and tolerability analysis

10.3.2.1 Analysis for primary variables

The analysis of safety and tolerability outcomes will be conducted in the safety population, defined as all subjects who received at least one dose of the investigational product (PRO-185), regardless of their adherence to the protocol (intention-to-treat, ITT, population).

Statistical analysis for the primary quantitative variables will be estimated using the Wilcoxon signed-rank test for a sample for the difference in measurements before and after treatment for visits 1 and 2, while the baseline visit (pre-PT) will be compared against the final visit, once the values have been adjusted with respect to their baseline within each individual.

For conjunctival hyperemia, the X^2 binomial test or Fisher's exact test will be used for expected values less than 5.

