3.1 Objectives

3.1.1 Main objective:

- To evaluate the safety and tolerability of PRO-185 ophthalmic solution in ophthalmologically healthy subjects.

3.1.2 Specific objectives:

- To evaluate the safety of PRO-185 ophthalmic solution by measuring the incidence of subjects who present an increase of > 5 mmHg in intraocular pressure after 20 minutes of application compared to the initial value.
- To evaluate the safety of PRO-185 ophthalmic solution by measuring the incidence of subjects experiencing a heart rate variation of >15 beats per minute 20 minutes after application.
- To evaluate the safety of PRO-185 ophthalmic solution by measuring the incidence of subjects with an increase in systolic blood pressure of >15 mmHg or >10 mmHg in diastolic blood pressure 20 minutes after application.
- To assess tolerability by the incidence of grade 3 and 4 conjunctival hyperemia.
- To assess tolerability by the incidence of pharmacological mydriasis.
- Evaluate tolerability by the incidence of expected and unexpected adverse events.

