3.2 Hypothesis

H_0 = PRO-185 ophthalmic solution is safe and tolerable for ophthalmic use, as it occurred in 20% or less of subjects with any of the following adverse events: increased intraocular pressure (IOP >5 mmHg), heart rate variation (>15 bpm), increased systemic blood pressure [>15 mmHg systolic (SBP) or >10 mmHg diastolic (DBP)], pharmacological mydriasis, or grade 3 and 4 conjunctival hyperemia.

$$H_0: p - p_0 \leq \delta$$

H_1 = PRO-185 ophthalmic solution is not safe or tolerable for ophthalmic application because more than 20% of subjects experienced any of the following adverse events: increased IOP (>5 mmHg), heart rate variation (>15 bpm), increased systemic blood pressure [>15 mmHg systolic (SBP) or >10 mmHg diastolic (DBP)], pharmacological mydriasis, or grade 3 and 4 conjunctival hyperemia.

$$H_1: p - p_0 > \delta$$

Comparisons will be made between pre- and post-treatment measurements from visits 1 and 2, and between measurements from the baseline visit (before PT application) and measurements from the

final visit. Only one of the adverse event values described in the hypothesis need be abnormal with a frequency >20% between the comparisons (pre-treatment with post-treatment; or pre-PT baseline with values from the final visit) for the null hypothesis to be rejected.

4. Study design

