7.4.4 Definition of variables, methods and scales for their measurement

Table iii. Operational definition of variables

Variable	Conceptual Definition	Operational Definition	Type of measurement	Reference value	Statistical test
Intraocular Pressure	Tonometry is the objective measurement of IOP, based on the force required to flatten the cornea or the degree of corneal indentation produced by a fixed force.	By means of Goldmann tonometry based on the Imberk -Fick principle.	Discrete quantitative	10 – 21 mmHg	Wilcoxon one-sample signed-rank test
Heart rate	Pulse is a measurement of HR, that is, the number of times the heart beats per minute.	With each heartbeat, the left ventricle contracts and expels blood into the aorta. This forceful expulsion of blood creates a wave that is transmitted to the periphery of the body through the arteries.	Discrete quantitative	60 – 100 bpm	Wilcoxon one-sample signed-rank test

Variable	Conceptual Definition	Operational Definition	Type of measurement	Reference value	Statistical test
		It is measured with an electronic blood pressure monitor or manually.			
Systemic blood pressure	It is the force exerted by blood against the walls of the arteries. SBP is the pressure inside the artery when the heart contracts and pumps blood through the body; while DBP is the pressure inside the artery when the heart is resting and filling with blood.	Measured with a blood pressure monitor and a stethoscope.	Discrete quantitative	SBP: 120 – 139 mmHg DBP: 80 – 89 mmHg	Wilcoxon one-sample signed-rank test
Pupillary diameter	The natural pupil of the human eye is usually approximately circular, for a given subject, the pattern of aberrations, diffraction, depth of field and retinal illumination depend on the pupil diameter, which in turn varies depending on the ambient lighting.	The pupillary diameter results from the balance between the pupillary sphincter muscle and the radial fibers of the iris, which have only autonomic innervation [33].	Continuous quantitative	2 – 6 mm	Wilcoxon one-sample signed-rank test
Conjunctival hyperemia	It is defined as the simplest reaction of the conjunctiva to a stimulus; a red	Direct observation. Classification using	Qualitative ordinal	Degrees: 0= Normal 1= Very mild 2= Mild	Binomial X²

Variable	Conceptual Definition	Operational Definition	Type of measurement	Reference value	Statistical test

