	appearance is observed secondary to vasodilation of the vessels of the conjunctiva of variable intensity.	the Efron scale (see appendix 16.1)		3= Moderate 4= Severe	
Changes in the AVMC	Spatial visual acuity is the ability to distinguish separate elements of an object and identify them as a whole. It is quantified as the minimum angle of separation (located at the nodal point of the eye) between two objects that allows them to be perceived as separate objects.	Snellen chart	Continuous quantitative	0.6 to 2.0	Wilcoxon one-sample signed-rank test
Changes in ocular surface staining	Detection of epithelial defects in the cornea and conjunctiva.	Direct observation with a slit lamp will be graded according to the SICCA (see annex 16.2) [34].	Discrete quantitative	0 to 12	Wilcoxon one-sample signed-rank test
Incidence of Chemosis	It is conjunctival edema, the result of an inflammatory reaction. It is classified as present or absent.	The evaluator will use a narrow beam of light at 60° and measure whether the conjunctiva separates by $\geq 1/3$ of the entire eyelid opening or if it extends beyond the gray line.	Nominal qualitative	Present / Absent	Binomial χ^2

Variable	Conceptual Definition	Operational Definition	Type of measurement	Reference value	Statistical test
Incidence of AE	Any adverse medical event that occurs in a patient or clinical research subject who has been administered a pharmaceutical product and that does not necessarily have a causal relationship with this treatment [35].	All AEs will be reported (according to the protocol) and not only those in which the PI suspects a causal relationship with the treatments.	• Discrete quantitative • Nominal qualitative	• Incidence • Seriousness (gravity) • Causality	Binomial χ^2
Respiratory rate	The process involves inspiration and expiration, diffusion of oxygen from the pulmonary alveoli to the blood and carbon dioxide from the blood to the alveoli, and the transport of oxygen to body tissues and organs.	RR is the number of breaths a person takes per minute at rest.	Discrete quantitative	12 – 16 rpm	Wilcoxon one-sample signed-rank test
Body temperature	A clinical parameter that reflects the physiological state of the body. It is the balance between heat production and heat loss.	Degree of heat or cold, expressed in terms of a specific scale, using a thermometer.	Continuous quantitative	36.7 – 37.4°C	Wilcoxon one-sample signed-rank test

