10.1.2 Size calculation

PRO-185 ophthalmic solution is expected to present in less than 20% of subjects any of the following AEs: increased IOP (>5 mmHg), heart rate changes (>15 bpm), increased systemic blood pressure (>15 mmHg in SBP or >10 mmHg in DBP), pharmacological mydriasis or grade 3 and 4 conjunctival hyperemia, 20 minutes after its application with respect to its initial value.

The sample size was calculated using the equation for a non-superiority proportion [53]. This equation is useful for non-inferiority/superiority tests, if we want to test whether a proportion (p) is not superior to a reference value, p_0 (20% in this case). The idea is that statistically significant differences between the proportion and the reference value cannot be of interest unless the difference is greater than a threshold δ (10% in this case). This type of calculation is useful in clinical studies where the value of δ is chosen based on clinical judgment and knowledge of the subject.

The hypothesis test is:

$$H_0: p - p_0 \leq \delta$$

$$H_1: p - p_0 > \delta$$

Equations

The calculation to estimate the sample size and power was performed using an online tool and following the equations [53]:

$$18 = p(1 - 0.2) \left(\frac{1.96 + z_{1-\beta}}{p - 0.2 - 0.1} \right)^2$$

$$1 - \beta = \Phi(z - 1.96) + \Phi(-z - 1.96), z = \frac{p - 0.2 - 0.1}{\sqrt{\frac{p(1 - 0.2)}{18}}}$$

Where:

n is the sample size (18)

p₀ is the reference value (0.20)

Φ is the function of the standard normal distribution

Φ⁻¹ is the function of the standard normal distribution

α is the Type I error (1.96)

β is the Type II error, which means that, 1-β (1-0.8) is the power

δ is the test margin (0.10)

According to the previous calculation, 18 subjects are estimated, increasing the calculation by 20% considering possible losses, 22 subjects are estimated to contribute OA to the study. This calculation is in accordance with the average number of subjects used in the clinical studies reviewed in the search performed in PubMed and Web of Science (24 subjects), where the incidence of adverse events was similar to that expected in this study.

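### For IOP, heart rate, blood pressure and pupil diameter, the planned primary test does not test the proportion of subjects over the limit, and no planned test of them uses the stated p0, margin or alpha

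*Protocol*

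**What the plan says.** The specific objectives (protocol 3.1.2) define safety as an incidence. For IOP the aim is to evaluate safety "by measuring the incidence of subjects who present an increase of > 5 mmHg in intraocular pressure", and heart rate and blood pressure are worded the same way. The sample size (10.1.2) is built to "test whether a proportion (p) is not superior to a reference value", with p0 = 20% and a margin of 10%. It adds that "statistically significant differences between the proportion and the reference value cannot be of interest unless the difference is greater than a threshold".

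The verdict is in 3.2 and is repeated in the synopsis: "Only one of the adverse event values described in the hypothesis need be abnormal with a frequency >20% between the comparisons" for the null hypothesis to be rejected. The comparisons are pre- versus post-treatment at visits 1 and 2, and baseline versus final visit.

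The analysis in 10.3.2.1 reads: "Statistical analysis for the primary quantitative variables will be estimated using the Wilcoxon signed-rank test for a sample for the difference in measurements". Table iii (7.4.4) likewise lists the "Wilcoxon one-sample signed-rank test" for IOP, heart rate, blood pressure and pupil diameter. SAP 6.2.1 has Kolmogorov-Smirnov, or Mann-Whitney where applicable. Alpha is 0.05 (10.3.1), with sidedness not stated; the sample size uses z = 1.96.

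There are categorical analyses. Hyperemia gets a binomial chi-square or Fisher test (10.3.2.1). AE incidence, a secondary variable, gets a binomial chi-square (Table iii, which notes "All AEs will be reported (according to the protocol) and not only those in which the PI suspects a causal relationship"). Section 10.3.1 plans frequencies and 2 x 2 tables. None of these names a null proportion.

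**The concern.** A signed-rank test asks whether changes are centred on zero. The primary question is how many subjects change by more than a clinical limit. The two can point in opposite directions, so the primary p-values for four of the five primary variables do not answer the primary objective.

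The statement that does answer it, the above-20% verdict, is not linked to a planned test or a confidence limit. What it does with 22 subjects is therefore nowhere examined, and it uses a different boundary from the sample size calculation. A final report could give Wilcoxon p-values, an observed-frequency verdict and a formal hypothesis that disagree, with no rule for which prevails.

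**Working it through.** **1. The plan's own figure.** Inputs: p0 = 0.20, margin 0.10 and z = 1.96 (protocol 10.1.2); power 0.80. The protocol gives no expected p, so I take 0.10 from SAP 4.1 as an assumption.
- SAP form: n = p(1−p)[(1.96 + 0.842)/(p − p0 − δ)]² = 0.09 × (2.802/0.20)² = 17.66, so 18.
- The protocol's printed p(1−0.2) form gives 0.08 × (2.802/0.20)² = 15.7.
- Inflation: 18 × 1.2 = 21.6, so 22.

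The figure reproduces, and it is a one-proportion calculation with boundary 0.20 + 0.10 = 0.30.

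**2. Test against criterion.** These are constructed data with 22 subjects and exact two-sided signed-rank tests, with ties.

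| Changes | Over the limit | Signed-rank result |
|---|---|---|
| HR: 4 at +16, 4 at −16, 7 at +5, 7 at −5 bpm | 8/22 (36%) | W+ = W− = 4 × 18.5 + 7 × 7.5 = 126.5; p = 1.0 |
| IOP: 7 at +6, 15 at −1 mmHg | 7/22 (32%) | W+ = 7 × 19 = 133, W− = 15 × 8 = 120; p = 0.80 |
| IOP: all 22 at +1 mmHg | 0/22 | p = 2 × 0.5²² = 4.8 × 10⁻⁷ |

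Heart rate is the clearest case, because 7.4.5.2 counts a change in either direction and rises and falls cancel in the test. The examples show that test and criterion can disagree, not how often they will.

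**3. The verdict as an observed frequency.** Above 20% means at least 5/22 (22.7%) or at least 4/18 (22.2%). Binomial probabilities for one criterion in one comparison:

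| True rate | Verdict | n = 22 | n = 18 |
|---|---|---|---|
| 20% | unsafe | P(X ≥ 5) = 45.7% | P(X ≥ 4) = 49.9% |
| 25% | passes | P(X ≤ 4) = 32.3% | P(X ≤ 3) = 30.6% |
| 30% | passes | P(X ≤ 4) = 16.5% | P(X ≤ 3) = 16.5% |

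A result of 4/22 passes although its exact 95% interval reaches 40.3%.

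The full rule fires on any criterion in any comparison, so the pass rates above are upper bounds. For one criterion over the three comparisons with n = 22, the range runs from full dependence to independence (both assumptions):
- Unsafe at a true 20%: 45.7% to 1 − 0.543³ = 84%.
- Pass at a true 25%: 32.3% to 0.3235³ = 3.4%.
- Pass at a true 30%: 16.5% to 0.1645³ = 0.4%.

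**4. Verdict against formal hypothesis.** Section 3.2 prints H0 as p − p0 ≤ δ without values. With the values from 10.1.2, H0 is p ≤ 0.30. An exact test with 22 subjects rejects at:
- 12 or more at one-sided 0.025: P(X ≥ 12 | 0.30) = 0.014;
- 11 or more at one-sided 0.05: P(X ≥ 11 | 0.30) = 0.039.

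The verdict rejects at 5 or more. So 5 to 11 events (5 to 10 at one-sided 0.05) are unsafe by the verdict but do not reject the formal H0.

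**The case against.** The strongest reply is that the plan does contain the elements of a proportion test. The verdict is worded as rejecting a null that names 20%; p0, the margin and alpha are all stated. A reader might infer that the plan has no null proportion or alpha at all, and the documents do not support that. What is missing is a planned test of these four variables that uses them.

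Second, per-subject thresholds largely exist. An IOP rise above 5 mmHg (7.4.5.1) and a pupil change above 2 mm (7.4.5.4) are adverse events, so both enter the AE-incidence analysis. That stands, but the analysis is secondary and has no null proportion. For heart rate and blood pressure, 7.4.5.2 and 7.4.5.3 call the changes abnormal yet define AE handling by absolute levels, while 3.2 and 10.1.2 call the changes adverse events. That route therefore need not capture these two criteria.

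Third, the Wilcoxon result changes no verdict. Under 3.2 the three constructed data sets would be unsafe, unsafe and safe whatever the p-value. This is correct: a reader might infer that the wrong test produces a wrong safety conclusion, but the documents show only a primary p-value that answers a different question.

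Fourth, a rate near 50% exactly at the threshold is what any observed-frequency cut-off gives. This is also correct, and 45.7% should not be read as the error rate of the whole rule, which is more prone to call the product unsafe. Nor is 3.2 contradictory on its own, since the 30% boundary needs the values from 10.1.2.

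**Conclusion.** The point holds in this limited form. For four of the five primary variables the only planned primary test does not address the proportion that the objectives, hypothesis and sample size are about, and no other section repairs it. This rests on the text alone and needs no distributional assumption.

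The verdict is an unexamined observed-frequency rule. The size given for it rests on binomial sampling with 22 (or 18) evaluable subjects, one criterion and one comparison; the three-comparison ranges rest on the stated dependence extremes. The conflict between 20% in 3.2 and 30% in 10.1.2 is definite. Its width, 5 to 11 or 5 to 10 events of 22, depends on which alpha is meant. It should be corrected before analysis.

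**What to change.** 1. Derive a subject-level yes/no indicator for each criterion, and for the composite if that is what is meant. State how the two eyes and the visits combine into one value. Reconcile whether the heart rate and blood pressure changes are adverse events.
2. Make count/N with an exact 95% confidence interval the primary analysis, read against one boundary. First reconcile 20% (protocol 3.2), 30% (protocol 10.1.2) and 10% (SAP 3.2), and the opposite H0 wording: safe in the protocol, not safe in the SAP.
3. Keep the Wilcoxon as supportive, and remove Kolmogorov-Smirnov and Mann-Whitney from the SAP.
4. A formal exact test to show safety is optional. If it is used, state its power. At a true 10% (SAP 4.1) and one-sided 0.025:

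| Boundary | n = 18: events allowed, power | n = 22: events allowed, power |
|---|---|---|
| 30% | at most 1, 45% | at most 2, 62% |
| 20% | 0, 15% | 0, 10% |
| 10% | – | none: even 0/22 has probability 0.9²² = 0.098 |

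5. Do not simply attach an exact test to H0 = safe. Against 20% it rejects only at 9/22 or more (P = 0.020), so 8/22 (36%) would still count as safe, which is more lenient than the present rule.

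Cost: text changes to the protocol (synopsis, 3.2, Table iii, 10.1.2, 10.3) and to the SAP, the committee approval that protocol 11.2 requires for substantial amendments, and a short derivation program. No new measurements are needed, and the estimation analysis needs no added subjects. A formal test at this size would have to accept the power shown.

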5.1 Eligibility criteria

5.1.1 Inclusion criteria

- Be clinically healthy
- Have the ability to voluntarily grant signed informed consent
- Be able and willing to comply with scheduled visits, treatment plan, and other study procedures
- Be between 18 and 45 years old.
- Women of childbearing potential must ensure continued use (started \geq 30 days prior to signing the ICF) of a hormonal contraceptive method or intrauterine device (IUD) during the study period.
- Have a best-corrected visual acuity of 20/30 or better in both eyes.
- Have vital signs within normal parameters.
- Have an intraocular pressure \geq 10 and \leq 21 mmHg.

5.1.2 Exclusion criteria:

- Be a user of topical ophthalmic products of any kind.
- Being allergic to naphazoline or having a history of intolerance to nasal decongestants or ocular vasoconstrictors.
- Have a history of a suspected diagnosis of primary angle closure, primary angle closure, or angle-closure glaucoma.
- Having iridotomies or waiting for iridotomies.
- Have conjunctival hyperemia grade 3 and 4 on the Efron scale.
- Have ocular surface staining with a value equal to or greater than 3 on the SICCA scale in either eye.
- Being a user of medications or herbal products, by any other route of administration.
- For women: be pregnant, breastfeeding, or planning to become pregnant during the study period.
- Having participated in clinical research studies 90 days prior to inclusion in this study.
- Having previously participated in this same study.
- Be a contact lens user who cannot discontinue use during the study.
- Having a history of any chronic-degenerative disease, including diabetes and high blood pressure.
- Present inflammatory or infectious disease, active at the time of entering the study.
- Present unresolved injuries or traumas at the time of entering the study.
- Have a history of any type of eye surgery
- Having undergone non-ophthalmological surgical procedures in the last 3 months.

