10.1 Sample size calculation

The sample size calculation was based on the study's primary objective: to evaluate the safety and tolerability of PRO-185 ophthalmic solution (naphazoline hydrochloride 0.03% and hypromellose 0.2%) in clinically healthy subjects. To meet the study's primary objective, an estimated 22 subjects will contribute OA to the study.

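### By subject, the below-5 rule sends hyperemia to Fisher's exact test, which cannot test one proportion against 20% and ignores the pre/post pairing

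*Protocol*

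**What the plan says.** - **Test.** Protocol 10.3.2.1 names the binomial chi-square for hyperemia and adds that Fisher's "exact test will be used for expected values less than 5". The synopsis allows Fisher when applicable. Table iii lists only the binomial chi-square. SAP 6.2.1 and SAP Table 2 give Pearson's chi-square or Fisher.
- **Tables.** For qualitative variables, Protocol 10.3.1 says: "For these, 2 x 2 frequency tables will be constructed".
- **Hypothesis.** Protocol 3.2 sets 20% of subjects as the limit and rejects the null hypothesis if one listed event "need be abnormal with a frequency >20"%. Grade 3 and 4 hyperemia is one of the listed events. SAP 3.2 uses 10%.
- **Comparisons.** Pre- versus post-treatment at visits 1 and 2, and baseline versus final visit, all within subject (Protocol 3.2).
- **Entry.** Protocol 5.1.2 excludes anyone who meets: "Have conjunctival hyperemia grade 3 and 4 on the Efron scale".
- **Size.** Protocol 10.1 says "an estimated 22 subjects will contribute OA to the study" (both eyes). Section 10.1.2 gives 18 before losses, a reference of 0.20 and a margin of 0.10.
- **Paired binary test.** The current protocol names none, and its change history records that McNemar was withdrawn. The SAP keeps McNemar for chemosis only.

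**The concern.** Hyperemia is a primary variable, and the question asked of it is whether one proportion exceeds a fixed 20%. The fallback for small expected counts is a two-group test in a study with one group. If that fallback operates at the planned size, the reported p-value does not address the hypothesis. The only two columns available to it are repeated measurements on the same people, which it would treat as unrelated. A significant result could then be reported as evidence against the 20% limit when it shows only that the rate is not zero.

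**Working it through.** **Plan's own size.** n = p(1 - p)[(1.96 + 0.84)/(p - p0 - delta)]^2. The protocol gives no value for p. Assuming 0.10 (the SAP's AE proportion), with p0 = 0.20 and delta = 0.10, n = 17.66, rounded to 18. Then 18 x 1.2 = 21.6, rounded to 22. The variance as printed, p(1 - 0.2), gives 15.7, rounded to 16. The rest of the check uses only 18 and 22.

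**Does the rule fire, by subject?**
- One sample against 20%: 22 x 0.20 = 4.4 and 18 x 0.20 = 3.6. Both are below 5 whatever the data. It takes 25 subjects to reach 5.0.
- Before/after 2 x 2 table with no baseline events: the smallest expected count is half the later events, so the rule fires unless there are 10 or more. With 22 subjects, the probability of 10 or more is 0.00002 at a true rate of 10%, 0.6% at 20% and 9.2% at 30%.

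**What Fisher then tests.** Take baseline 0/22 and final 5/22 (smallest expected count 2.5).
- Fisher, two-sided: 2 x C(22,5)/C(44,5) = 2 x 26,334/1,086,008 = 0.0485.
- Exact binomial for more than 20%: P(X >= 5 | 22, 0.20) = 1 - 0.5429 = 0.457.
- Exact McNemar, 5 discordant pairs all one way: 2 x 0.5^5 = 0.0625.
- Clopper-Pearson 95% CI for 5/22: 7.8% to 45.4%.

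| Final-visit events (baseline 0/22) | Fisher p | Binomial p for >20% | McNemar p |
|---|---|---|---|
| 4 (18.2%) | 0.108 | 0.668 | 0.125 |
| 5 (22.7%) | 0.0485 | 0.457 | 0.0625 |
| 8 (36.4%) | 0.0036 | 0.056 | 0.0078 |
| 9 (40.9%) | 0.0014 | 0.020 | 0.0039 |

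Fisher is significant from 5/22. The exact one-sided binomial test at 0.05 needs 9/22. If the true rate is 20%, which Protocol 3.2 counts as safe, 5 or more of 22 occurs with probability 0.457. Reading Fisher as a test of the 20% limit would therefore give a false signal about 46% of the time in this comparison, against a nominal 5%.

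**The case against.** Several parts of the opposing case stand.

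- **A reader might infer that the rule fires in every case.** The documents do not support that. Both eyes contribute and the analysis unit for hyperemia is not stated: by eye, 44 x 0.20 = 8.8. Against reference plus margin (30%), 22 x 0.30 = 6.6. Neither triggers the rule, nor does a before/after table with 10 or more events. But 3.2 counts subjects and states 20% in words, and on that reading the rule fires.
- **A reader might infer that the two eyes are compared as independent groups.** No right-versus-left comparison is planned. The ignored pairing is between occasions in the same subject.
- **A reader might extend the zero before-count to visits 1 and 2.** It is guaranteed only at baseline. The pre-treatment checks at those visits follow days of home dosing.
- **A reader might conclude that Fisher contradicts the 20% criterion at 5/22.** It does not: 22.7% exceeds 20%, so Fisher and the observed-frequency rule in 3.2 agree there, and at n = 22 both change between 4 and 5 events. That match is an accident of the sample size: 4/18 is 22.2%, yet Fisher gives p = 0.104.
- **The text is loose.** The synopsis says when applicable, and Table iii names only the binomial chi-square, so a one-proportion method is already in the protocol. That does not remove the fallback in 10.3.2.1, which is the only stated remedy for small counts.

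**Conclusion.** The hyperemia test is wrong as written. By subject against 20%, the expected count at the planned size is 4.4 (3.6 with 18 evaluable), so 10.3.2.1 calls for a test that can neither use the 20% reference nor respect the pairing. In the baseline versus final comparison the gap is p = 0.0485 against 0.457 for the same 5/22. This rests on the subject as the unit, 20% as the reference, complete data on 22 subjects and, for the worked example, no grade 3 or 4 at baseline. The defect is in the choice of test. The documents do not support saying that Fisher would apply under every unit and reference, or that its result must oppose the 20% rule.

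**What to change.** 1. In Protocol 10.3.2.1 and the synopsis, and in SAP 6.2.1 and Table 2, delete the chi-square/Fisher choice for hyperemia. Specify an exact one-sample binomial test by subject against the protocol's 20% reference, with a Clopper-Pearson 95% CI. Align Protocol Table iii. No expected-count rule is then needed.
2. Define the unit: a subject counts if either eye is grade 3 or 4.
3. Reconcile the test with the observed-frequency wording in 3.2, the 0.10 margin in 10.1.2, and the SAP's 10% and its reversed verbal hypotheses. State the direction: with 22 subjects, showing more than 20% at one-sided 0.05 needs at least 9 events (exact level 0.020), and showing less than 20% needs at most 1 (exact level 0.048).
4. If a before/after test is also wanted, use exact McNemar on the paired binary outcome.
5. Protocol 10.3.2.2 carries the primary analysis over to secondary variables. The 20% limit does not cover chemosis or general AE incidence, and no reference rate is stated for them. Drop Fisher there and report incidence by subject with an exact CI.

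The cost is wording in both documents, with no change to sample size, visits or assessments.
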